APPENDIX II: FINACEA® PACKAGE INSERT

MedDRA	Medical Dictionary for Regulatory Activities
mITT	Modified Intent to Treat
mm	Millimeter
PI	Principal Investigator
PP	Per Protocol
PT	Preferred Term
TEAE	Treatment Emergent Adverse Event
SAE	Serious Adverse Event
SOC	System Organ Class
UV	Unscheduled Visit

1. INTRODUCTION

The purpose of this statistical analysis plan (SAP) is to provide details of the statistical analyses that have been outlined within the protocol "A Multicenter, Double-blind, Randomized, Parallel-group, Vehicle-Controlled Study to Evaluate the Safety and Clinical Equivalence of a Generic Azelaic Acid Foam, 15% and the Reference Listed Finacea® (azelaic acid) Foam, 15% in Patients with Moderate Facial Rosacea" dated January 27, 2016.

Marketed by Bayer HealthCare, Finacea® (azelaic acid) Foam, 15% is a safe and effective topical therapy used for the treatment of moderate facial rosacea. Actavis Laboratories UT has developed a generic formulation of azelaic acid 15% foam and the current study is designed to evaluate the safety and efficacy of this formulation. This randomized, vehicle-controlled, parallel-group, multicenter, double-blind study was designed to evaluate the therapeutic equivalence and safety of a generic Azelaic Acid Foam, 15% and Finacea® (Azelaic acid) Foam 15%, in the treatment of moderate facial rosacea, and to demonstrate the superiority of the efficacy of the two active foams over the vehicle control.

This document will give a description of the planned methods of the analysis.

2. OBJECTIVES

The objectives of this study are:

- to evaluate the therapeutic equivalence and safety of a generic Azelaic Acid Foam, 15% and Finacea® (azelaic acid) Foam, 15% in the treatment of moderate facial rosacea;
- to demonstrate superiority of the efficacy of the two active foams over the vehicle control.

3. STUDY OVERVIEW

3.1 Study Design

Up to 1010 patients will be enrolled in the study to randomize 924 patients to obtain at least 840 modified Intent-to-Treat (mITT) patients in a 1:1:1 ratio (280:280:280 patients, respectively) to each treatment group and 672 (224:224:224) evaluable subjects in the Per protocol (PP) population. Patients will be assigned in a 1:1:1 ratio to treatment with the Test product, Azelaic Acid Foam, 15% (Actavis Laboratories UT), the Reference product,

Finacea® (Azelaic acid) Foam, 15% (Bayer HealthCare) or the Vehicle control (Actavis Laboratories UT) in this multicenter, double-blind, randomized, vehicle-controlled, parallel-group study.

The assigned Investigational Product (IP) will be self-applied topically to the entire facial area (cheeks, chin, forehead, and nose) twice daily for 84 consecutive days. The IP should be gently massaged into the affected areas on the face twice daily, in the morning and evening after the patient's face has been washed with a mild cleanser and patted dry with a soft towel. Patients will be required to use diaries to document study treatments, any missed treatments and the occurrence of all adverse events.

The duration of each patient's participation in the study will be 84 days. Scheduled study visits will include: Visit 1 (Baseline Visit, Day 0), Visit 2 (Day 28 ± 4 days), Visit 3 (Day 56 ± 4 days), and Visit 4 (End of Treatment, Day 84 ± 4 days). A window of ± 4 days will be considered acceptable for each scheduled visit following the baseline visit.

If the Principal Investigator determines that the patient's condition has worsened to the degree that it is unsafe for the patient to continue in the study, the patient may be discontinued from the study as a treatment failure and the patient may be treated using the standard care.

An Unscheduled Visit is allowed at any time, for any reason, if in the Principal Investigator's opinion, it is warranted. If a patient is discontinued from the study during an Unscheduled Visit, the Unscheduled Visit will be referred to as an Early Discontinuation Visit and all procedures scheduled for Visit 4 will be performed. If the Unscheduled Visit is not an Early Discontinuation Visit (i.e., the patient will continue to take part in the study), then the activities performed will depend on the reason for the unscheduled visit and will be left to the discretion of the Investigator. The Investigator should perform any activities necessary to appropriately evaluate the patient at this Unscheduled Visit. If the Unscheduled Visit is due to an AE, the Investigator will determine whether additional visits are needed.

At Visit 1, an informed consent will be obtained from the potential study patient before any study procedures take place. After the patient has been consented, the patient's medical history will then be documented, including the patient's concomitant medications. A urine pregnancy test will be performed for all female patients of child-bearing potential. A baseline

facial rosacea grade will be assigned to the patient using the Investigator's Global Evaluation (IGE) and a baseline lesion count will be performed. The patient will undergo a physical examination, including the recording of vital signs. The patient will be evaluated for signs and/or symptoms of erythema and telangiectasia. The patient will be reviewed against the inclusion/exclusion criteria. Blinded IP will be dispensed to patients who meet all of the inclusion and exclusion criteria. Patients will be instructed on the application of IP and completion of patient diaries.

Patients will return to the study site for Visit 2, Visit 3, and Visit 4. The patient's concomitant medications will be reviewed and documented. A urine pregnancy test will be performed for female patients of child-bearing potential. The patient's facial rosacea will be assessed using the IGE, the patient's lesions will be counted and all results will be documented. The signs and/or symptoms of local irritation will be evaluated for the patient and any other adverse events will be documented. The patient will bring their used IP and their study diaries to each study visit after the baseline visit. Compliance with drug applications will be assessed at each visit after the baseline visit. New can(s) of IP will be dispensed during Visit 2 and Visit 3. In addition, all IP and diaries will be collected from the patient during each scheduled visit or the Early Discontinuation Visit.

3.2 Sample Size

The sample size for this protocol is based on published data (Finacea® Summary Basis of Approval); Finacea® produced a percent reduction for inflammatory lesions of approximately 55% and the Vehicle had a percent reduction of 40% after 12 weeks of treatment.

The anticipated standard deviation for inflammatory lesions is < 47%. A sample size of n1 = 280, n2 = 280, and n3 = 280 evaluable mITT patients (1:1:1 ratio) to provide at least 224 PP patients in each of the Test and Reference treatment groups should provide at least an [REDACTED] of showing that, the 90% confidence interval on the Test/Reference ratio of percent reduction from baseline is contained within the interval 0.800 to 1.250 in the PP population and at the same time demonstrating that the Test and Reference products are superior to the vehicle in the mITT population.

In this study, enrolled patients will be randomized in the ratio of 1:1:1 to test, reference and vehicle treatments. It is anticipated that 75% of the mITT patients will qualify for the PP population. Accordingly, approximately 924 patients will be randomized in the study to obtain at least 840 mITT patients in a 1:1:1 ratio (280:280:280 patients, respectively) to each treatment group.

3.3 Randomization and Unblinding Procedures

Patients will be randomly assigned in a 1:1:1 ratio to receive the Test product, the Reference product, or the Vehicle control, respectively. The randomization assignment will be a block randomization, with 3 sequential patient numbers in each block.

An independent third party will generate the randomization code using SAS and hold it throughout the conduct of the study in order to minimize bias. A sealed copy of the randomization scheme will be retained at each study site.

The treatment assignments will remain blinded until the final database is locked. The contents of the cans of IP may not be viewed by the PI, any Sub-investigator, evaluator or any other (blinded) member of the site staff.

In the event of an emergency, the patient-specific treatment may be identified; however, every effort should be made to maintain the blind.

In the event of unblinding, the patient should be excluded from the PP population. The Sponsor or designee must be notified in the event the blind is broken.

4. STUDY ENDPOINTS/OUTCOMES

Primary Efficacy Endpoint

The primary efficacy endpoints are the percent change from Baseline to Week 12 in the inflammatory (papules and pustules) lesion count.

Secondary Efficacy Endpoint

The secondary endpoint is the clinical response of "success" or "failure" at Week 12 on the IGE. Success is defined as an IGE score of 0 (clear) or 1 (almost clear). Any patient who is not considered to be a success will be considered to be a failure.

5. HYPOTHESES TESTING

Hypothesis of Equivalence (Primary Endpoint)

A two-sided, 90% confidence interval on the test/reference ratio for mean percent change from Baseline in the inflammatory lesion count will be constructed using Fieller's method. The estimates of treatment means and standard errors will be obtained from a two-way Analysis of Variance of the Test and Reference results, using a statistical model containing terms for treatment and center. Non-parametric methods will be used if the skewness factor for the residuals from the Analysis of Variance (ANOVA) model is outside the range -2 to +2. Bioequivalence will be established if the 90% confidence interval for the ratio of test/reference means is contained within the interval [0.80, 1.25].

Hypothesis of Equivalence (Secondary Endpoint)

A two-sided, continuity-corrected, 90% confidence interval on the Test-to-Reference difference for the proportion of patients with treatment success on the IGE will be constructed. Bioequivalence will be established if the 90% confidence interval for the difference is contained within the interval [-0.20, +0.20].

Hypothesis of Superiority (Primary Endpoint)

The null hypothesis to be tested is that there is no difference in the mean percent change (reduction) from baseline in the inflammatory lesion count between the active treatment and the Vehicle treatment. The hypothesis testing will be performed separately for the Test treatment versus the Vehicle treatment and for the Reference treatment versus the Vehicle treatment using ANOVA under assumption of normal error and homogeneity of variance. Only data for the relevant two treatment arms will be included in each ANOVA. Similarly, to bioequivalence, non-parametric methods will be used if the skewness factor for the residuals from the ANOVA model is outside the range -2 to +2.

Superiority will be established if the mean percent change (reduction) from Baseline in the inflammatory lesion count for each active treatment is greater than, and statistically different from ($p < 0.05$, two-sided), that for the Vehicle.

Hypothesis of Superiority (Secondary Endpoint)

The null hypothesis to be tested is that there is no difference in the proportions of patients with treatment success on the IGE. The evaluation of superiority will be conducted separately for the Test treatment versus the Vehicle treatment and for the Reference treatment versus the Vehicle treatment. The analysis will be conducted using two-sided, $\alpha = 0.05$, Fisher's exact test.

Superiority will be established if the success proportion for each active treatment is greater than, and statistically different from, that of the Vehicle.

6. ANALYSIS SUBSETS

6.1 Safety Population

The safety population includes any individual who was randomized into the study and has evidence of usage of at least one dose of IP according to subject's diary. For patients who are randomized but fail to return their diary card and for whom no evidence of study drug use is available, the following conservative approach will be applied:

- if some safety or efficacy data for these patients is available after Visit 1, they will be included in the Safety population;
- if no safety or efficacy data for these patients is available after Visit 1, they will be considered lost to follow-up and excluded from the Safety population.

The Safety population will be the primary population for the safety analysis.

6.2 Modified Intent to Treat Population (mITT Population)

The mITT population includes all Safety population patients who met all inclusion/exclusion criteria and return for at least one post-baseline efficacy evaluation. This population will be considered as supportive for testing the clinical equivalence and as definitive while testing the superiority.

6.3 Per Protocol Population (PP Population)

The PP population includes all mITT patients who apply 75% to 125% of the scheduled applications of the assigned product for 12 weeks, do not miss more than 6 consecutive applications, return for the 12-week evaluation within +/- 4 days OR have discontinued from the study due to lack of treatment effect (after completing at least 8 weeks of compliant study medication use), and have no protocol major violations.

Patients who are discontinued prematurely from the study due to lack of treatment effect after completing at least 8 weeks of compliant study medication use and without major protocol violations will be included in the PP population as treatment failures (i.e., non-responders) even if they do not have Week 12 evaluation within the visit window or at all. An LOCF approach will be used for imputing missing lesion counts in these PP patients and they will be considered as failures in the IGE evaluations.

Patients discontinued prematurely for other reasons (including those who discontinue due to lack of treatment effect with less than 8 weeks of treatment) will be excluded from the PP population, but included in the mITT population, using LOCF.

Patients can be additionally excluded from the PP population due to non-compliance, if the Investigator's and Sponsor's review of their dosing times suggests a clinically meaningful departure from a twice-daily dosing pattern.

For the purpose of determining the PP status of the patient, a "major protocol violation" is any patient or investigator activity that could have possibly interfered with the therapeutic administration of the treatment or the precise evaluation of the treatment efficacy.

The PP population will be considered as definitive for testing the clinical equivalence and as supportive while testing the superiority.

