Data Sets to be Analyzed:	
Three patient populations are defined as follows:
 
 1. The Safety Population includes any patient who was randomized in the study and had at least one dose of Investigational product. 2. The Modified Intent-to-Treat (mITT) Population includes all randomized patients who met all inclusion/exclusion criteria, received study treatment, and returned for at least one post-baseline visit with lesion count. 3. The Per-Protocol (PP) Population includes all randomized patients who met all inclusion/exclusion criteria, were compliant with the assigned study treatment (who applied 75% to 125% of the scheduled applications), returned to the study site for the primary endpoint visit (12 week evaluation) within +/- 4 days OR discontinued from the study as a treatment failure and did not have any protocol violations. 4. Patients who are discontinued early from the study due to lack of treatment effect after completing at least eight weeks of treatment will be included in the mITT and PP population as treatment failures (i.e., non-responders) and the change in inflammatory lesion count from the baseline visit to the last completed visit prior to discontinuation due to lack of efficacy will be carried forward in the primary endpoint analysis. In addition, patients whose condition worsens after completing at least eight weeks of treatment and require alternate or supplemental therapy for the treatment of facial rosacea during the study will be discontinued, included in the PP population analysis, and provided with effective treatment. A last observation carried forward (LOCF) approach will be used for imputing missing efficacy results in these PP patients and they will be considered as failures in the IGE evaluations. 
Patients discontinued prematurely for other reasons will be excluded from the PP population, but included in the mITT population, for which missing efficacy data will be imputed using LOCF.
 
For the purpose of determining the per-protocol status of the patient, a “protocol violation” is any patient or investigator activity that could have
			

	
possibly interfered with the therapeutic administration of the treatment or the precise evaluation of treatment efficacy.
 
Efficacy analyses will be performed on the mITT and per-protocol populations. All efficacy data will be listed by treatment and patient in data listings.

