11.3.4 Patient Discontinuation Criteria

Investigators are urged to enroll only those eligible patients who are likely to complete the entire study and who are willing to comply with the protocol-specified procedures. It is the right and duty of the investigator to interrupt the treatment of any patient whose safety and well-being are determined to be at risk, or who may be experiencing unmanageable factors that may interfere with the study procedures and/or the interpretation of study results. Such patients should be withdrawn from the study rather than continued under a modified regimen.

Discontinuation is permanent; once a patient is discontinued, he/she shall not be allowed to enroll again.

A patient may be discontinued from the study for any of the following reasons:

1. Patient decision/withdrawal of consent;
2. Adverse event, including intercurrent illness, which required study discontinuation;
3. If the patient's condition has worsened to the degree that the Principal Investigator feels it is unsafe for the patient to continue in the study;
4. If the patient's drug code is unblinded;
5. Insufficient therapeutic response (after at least 8 weeks of compliant treatment);
6. If a patient misses more than 6 consecutive doses;
7. If the subject misses more than 1 required visit;
8. Significant protocol violation;
9. If the patient is lost to follow-up;
10. If the patient becomes pregnant;
11. If the patient becomes a prisoner or becomes involuntarily incarcerated;
12. Any other reason that may affect the outcome of the study or the safety of patients; or
13. Termination of the study by the Sponsor.

A patient that discontinues from the study will not be replaced.

A significant protocol violation is defined as any patient or Investigator activity that could have possibly interfered with the therapeutic administration of the treatment or the precise evaluation of treatment efficacy.

The reasons for a patient discontinuation will be documented. If a patient is discontinued from the study for any reason, the procedures scheduled for Visit 4 will be completed and any outstanding data and study drug should be collected, if possible. Information, in addition to the reason for discontinuation and the date of removal, will be documented on the Electronic Case Report Form (eCRF).

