12.4.4 Datasets to be Analyzed

Three analysis populations will be used in the analysis of the clinical data and they are defined as follows:

1. The Safety population includes any individual who was randomized into the study and used at least one dose of Investigational Product.
2. The mITT population includes all randomized patients who met all inclusion/exclusion criteria, received study treatment, and returned for at least one post-baseline visit with lesion count.
3. The PP population includes all randomized patients who met all inclusion/exclusion criteria, were compliant with the assigned study treatment (who applied 75% to 125% of the scheduled applications), returned to the study site for the primary endpoint visit (12 week evaluation) within +/- 4 days OR discontinued from the study as a treatment failure (after completing at least 8 weeks of compliant study medication use), and did not have any protocol violations. The compliance will be verified by the use of patient diaries. Patients who are discontinued early from the study due to lack of treatment effect, or who require alternate or supplemental therapy to treat their rosacea, after completing at least eight weeks of treatment will be included in the mITT and PP population as treatment failures on the IGE and their change in inflammatory lesion count from baseline to the last completed visit prior to discontinuation will be carried forward (LOCF).

Patients discontinued prematurely for other reasons will be excluded from the PP population, but included in the mITT population, with missing efficacy data imputed using LOCF.

For the purpose of determining the per-protocol status of the patient, a “protocol violation” is any patient or investigator activity that could have possibly interfered with the therapeutic administration of the treatment or the precise evaluation of treatment efficacy.

Efficacy analyses will be performed on the mITT and Per-protocol populations.

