7.5.2 Analyses of Primary Endpoint

At each visit, an Investigator will assess the patient's facial rosacea by counting the number of pustules, papules, and nodules. The number of pustules, papules, total number of inflammatory lesions (pustules and papules) and nodules will be reported on the CRF.

Missing Week 12 assessments will be imputed as follows. In the mITT analysis, if a patient discontinues the study prior to Week 12 or misses the Week 12 assessment for any other reason, the LOCF rule will be used to impute the number of lesions. In the PP analysis, if a patient discontinues the study prior to Week 12, due to lack of treatment effect, after at least 8 weeks of treatment, the LOCF rule will be used to impute the number of lesions. If a patient is missing the Week 12 assessment for any other reason, the patient will be excluded from the PP population.

The baseline lesion count will be defined as the results from the latest examination prior to the start of study drug therapy. For each post-baseline visit the change from Baseline and percent change from Baseline in the total number of inflammatory lesions will be calculated. The baseline value, timepoint value, change from baseline, and percent change from baseline at the timepoint will be analyzed using descriptive statistics and will be tabulated by site, visit, and treatment group.

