8. CHANGES FROM PROTOCOL-SPECIFIED ANALYSES

There are no changes from the protocol-specified analyses.

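### The SAP carries over only part of the protocol's rule for keeping failures after 8 weeks in the PP population, so some patients who need other rosacea therapy may drop out of the definitive equivalence analysis, and the change is not declared

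*SAP*

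**What the plan says.** **Protocol.** Section 12.4.4 puts into mITT and PP, as IGE failures with the last lesion change carried forward, patients discontinued for lack of effect "or who require alternate or supplemental therapy to treat their rosacea, after completing at least eight weeks of treatment will be included". The synopsis gives the second group its own sentence: "patients whose condition worsens after completing at least eight weeks of treatment and require alternate or supplemental therapy for the treatment of facial rosacea" "will be discontinued, included in the PP population analysis, and provided with effective treatment", with LOCF for lesion counts and failure on the IGE. The PP definition in 12.4.4 also admits anyone discontinued as a treatment failure after 8 compliant weeks, and Section 11.2 applies that label to discontinuation for worsening.

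**SAP.** The PP definition in 6.3 requires the Week 12 visit in window "OR have discontinued from the study due to lack of treatment effect (after completing at least 8 weeks of compliant study medication use"). All other premature discontinuations are excluded from PP and kept in mITT by LOCF. Three further places use the same narrow condition:

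- 7.5.2, on the primary endpoint, allows LOCF in PP for lack of effect only, then adds: "If a patient is missing the Week 12 assessment for any other reason, the patient will be excluded from the PP population".
- 7.5.3 limits automatic IGE failure, in PP and in mITT, to lack of effect after 8 compliant weeks.
- 7.4 item 9 exempts only lack-of-effect patients from the major deviation for not attending Visit 4.

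SAP 6.3 makes PP definitive for equivalence. SAP 8 states: "There are no changes from the protocol-specified analyses".

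**The concern.** The two documents define the definitive equivalence population differently, and the difference concerns patients who did badly. Excluding a patient for needing other rosacea therapy conditions on a post-randomization outcome. If Test produces more such patients than Reference, leaving them out moves the Test/Reference ratio towards 1.

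There is a second effect in mITT, which is definitive for superiority on the IGE. The protocol counts these patients as failures, whereas SAP 7.5.3 carries their last IGE forward. The two rules give different answers only when the carried score is 0 or 1. That can happen if the last recorded visit preceded the worsening.

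**Working it through.** **1. Which patients are affected.** Protocol 11.3.4 lists the discontinuation reasons. Reason 3 is that the patient's "condition has worsened to the degree that the Principal Investigator feels it is unsafe for the patient to continue"; reason 5 is insufficient response after at least 8 weeks of compliant treatment. No reason names alternate therapy. For a patient who needs alternate rosacea therapy after 8 weeks:

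| Coded as | Protocol PP | SAP PP | Protocol mITT IGE | SAP mITT IGE |
|---|---|---|---|---|
| Lack of effect | In, failure | In, failure | Failure | Failure |
| Anything else, e.g. reason 3 | In, failure | Out | Failure | LOCF |

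The SAP does not say which reasons count as lack of effect.

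**2. Planning inputs** (protocol 12.1, SAP 3.2): reduction about 55% on the reference, SD below 47 (47 used), 224 PP patients per arm. The planned power is redacted, so there is no stated result to reproduce. The stated 75% retention from 280 mITT patients gives 0.75 × 280 = 210, whereas 224 is 0.80 × 280. The stated 224 is used here; this mismatch is a separate matter.

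**3. Base interval**, using the simplified Fieller formula in SAP 11.4 without a center term:

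- se = 47/√224 = 3.140, t (446 df) = 1.648
- g = t²·se²/55² = 0.00886
- half-term = (1.648/55)·√(3.140² + 3.140² − g·3.140²) = 0.133
- limits = (1 ∓ 0.133)/(1 − 0.00886) = **0.875 to 1.143**

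**4. Restoring k net extra Test patients, each with carried reduction x** (negative x means more lesions than at baseline):

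- m_t = (224·55 + k·x)/(224 + k)
- SS_t = 223·47² + 224(55 − m_t)² + k(x − m_t)²
- s² = (SS_t + 223·47²)/(446 + k), with 446 + k degrees of freedom
- se_t² = s²/(224 + k), se_r² = s²/224

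Example with k = 10, x = −50: m_t = (12,320 − 500)/234 = 50.51, s = 48.9, ratio 0.918, lower limit 0.795.

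| Carried change | k = 5: ratio, lower limit | k = 10: ratio, lower limit |
|---|---|---|
| 25% reduction | 0.988, 0.865 | 0.977, 0.855 |
| 0% | 0.978, 0.855 | 0.957, 0.836 |
| 25% worse | 0.968, 0.845 | 0.938, 0.816 |
| 50% worse | 0.958, 0.834 | 0.918, 0.795 |

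With x = 0 the lower limit is 0.803 at k = 19, just under 0.800 at k = 20 and 0.797 at k = 21. So about 20 to 21 net extra patients are needed, roughly 9% of 224.

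**5. Compliance denominator.** SAP 7.6.3 divides recorded applications by a fixed 168. The 75% rule therefore needs 0.75 × 168 = 126 applications, which is 63 days at two a day. A patient who stops at day 56 has at most 112/168 = 66.7% and fails 7.4 item 5. Read literally, this removes patients who leave between weeks 8 and 9 from PP even if the wording in 6.3 is corrected. It also removes lack-of-effect failures whom 6.3 intends to keep.

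**The case against.** A reader might infer that the SAP removes every worsened patient, that the definitive analysis loses the worst outcomes, and that a difference between products would be hidden. The documents do not support that, for four reasons.

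- **Exclusion depends on coding.** No SAP sentence excludes this group by name. Reason 3 mentions neither alternate therapy nor 8 weeks, and reason 5 is the only efficacy reason with an 8-week condition. A patient needing other therapy could well be coded under reason 5 and stay in PP. SAP 3.1 itself calls discontinuation for worsening a treatment failure. The eCRF reason list is not in the documents.
- **Other failures remain and an imbalance would be visible.** Lack-of-effect failures after 8 weeks are meant to stay in PP. The same equivalence analysis is run on mITT, which keeps the dropped patients by LOCF. Discontinuation reasons are tabulated by arm (SAP 7.2, protocol 12.5.7).
- **The prohibited-medication deviation is only a possibility.** SAP 7.4 item 1 applies to medication that clinical review judges critical to efficacy, and the synopsis wording allows the therapy to follow discontinuation.
- **Severe carried values may be unusual.** The protocol carries forward the last completed visit before discontinuation. That may be Visit 3, before the worsening, with lesions still below baseline.

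All four points stand, and they limit the size and certainty of the effect. They do not reconcile the texts. The protocol names the two groups separately in the synopsis and in 12.4.4, the SAP carries over one and gives no mapping, and SAP 8 says nothing changed. Two analysts, one following each document, could build different definitive populations.

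**Conclusion.** The mismatch is real and undeclared. The definitive equivalence analysis may lose some of the worst outcomes, with bias towards equivalence if Test has more of these patients than Reference. In mITT the same patients can receive a carried-forward IGE response where the protocol requires failure.

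The size cannot be established from the documents, which give no rate of such discontinuations. The illustration assumes equal means of 55% in the remaining patients, SD 47, 224 per arm, no center term, and all net extra patients in Test. On those assumptions five extra patients leave the lower limit well inside the margin (0.865 to 0.834). Of the eight scenarios shown, only ten extra patients all 50% worse than baseline crosses 0.80. The effect could therefore be negligible or, with a marked imbalance, decisive.

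This should be fixed; confidence is high on the wording difference and medium on its impact.

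**What to change.** Before unblinding, amend the SAP as follows:

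1. In 6.3, 7.5.2, 7.5.3 and 7.4 item 9, use the protocol 12.4.4 condition so that both groups are kept in PP with LOCF lesion counts and IGE failure, and both count as IGE failures in mITT.
2. State which eCRF discontinuation reasons map to treatment failure, identifying the second group from the recorded reason together with concomitant-medication data.
3. State that alternate therapy given because of such a discontinuation is not itself a PP-excluding deviation under 7.4 item 1.
4. In 7.6.3, for these patients and for lack-of-effect failures, compute compliance over the applications scheduled up to discontinuation instead of 168. End the count of doses missed after the last application at the same point.

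If the narrower SAP rule is intended, it should instead be declared and justified in SAP 8.

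**Cost.** Wording and programming. If the need for alternate therapy was not recorded as a reason, some patients may be hard to identify from concomitant medications alone, so the mapping needs a blinded review. The PP equivalence result may become slightly less favourable.
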